### **Recruitment & Retention Pilot:**

Power is provided for our primary aim. The analysis will compare the enrollment rates between the four intervention arms, and examine main and interaction effects. For SR arm, we expect a 28% of subjects who schedule an Intake will be eligible and enroll (based on existing data across the four studies). With the proposed sample of 576, we have >80% power ( $\alpha=.05$ ) to detect a difference between the SR arm and the IP and CM arms of 12%, corresponding to an OR of 1.75. For the interaction term, we have 80% power ( $\alpha=.05$ ) to detect a departure from additivity of the main effects corresponding to a ratio of odds ratios (ORR) of 5.5.

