**Recruitment & Retention Pilot.** This pilot study will utilize a randomized controlled trial design to evaluate two components of behavioral economic strategies to improve recruitment and retention. To be eligible for the pilot study participants must meet all eligibility criteria for one of the four participating studies (828958, 824061, **824860**, 828125), have a phone capable of receiving SMS messages, and consent to receive SMS messages. ~576 participants will be enrolled across the four participating research studies. All subjects will receive standard text messages and will be randomized to one of four groups (blocked within each study to ensure balanced groups): (1) Standard recruitment (SR): subjects will receive text messages ~2 days prior to their Intake visit with relevant information about the time, date, and location of the visit as well as contact information for study staff ("You have a study visit on [Date] at [Time]. Visit comp is \$10. Reply Y to confirm. See <http://j.mp/2222222> for reminders. Reply or appt may be canceled."); (2) SR + Information Provision (IP): Subjects will receive personalized messages designed to target injunctive norms regarding participating in research (e.g., "[Name], wondering why you should volunteer for research? Many find it a rewarding way to advance science and be a part of a community <http://j.mp/2222222>."); (3) SR + Contingency Management (CM): CM will be provided in the form of a randomization table with a high proportion of numbers that correspond to "chips" with little (\$1) monetary value. Participants draw by choosing numbers between 1-500 upon completion of an objectively verified target behavior (e.g., attending an Intake visit), and bonuses are often provided for continued performance. A similar strategy has been successful in augmenting visit compliance in several treatment studies. All text reminders will be delivered using the Way 2 Health (W2H) software platform. Upon completion of all requirements for a given visit, participants will receive 5 lottery "draws" for that visit. Attendance at all visits earns participants bonus draws upon completion of the study. Failure to attend a visit without prior approval or failure to complete all visit requirements results in no draws for that visit. The lottery contains 500 "chips" (numbers that correspond to monetary values within a table): 250 have a value of \$0, 219 have a value of \$1, 30 have a value of \$5, and 1 has a value of \$100. The study completion bonus will be 5 extra draws. Thus, at each visit, subjects will have the opportunity to make 5 draws, for maximum possible earnings of \$120; (4) SR + IP + CM (IC): In this group, subjects will receive the targeted text messages and receive CM. The design of our study allows us to examine each strategy independently as well as combined to evaluate the optimal approach.

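### Recruitment pilot: the stated interaction size (ratio of odds ratios 5.5) is about twice what 576 subjects detect at 80% power, and the >80% power fits the factorial main effects, not the SR-arm contrast as worded

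*Combined protocol and SAP*

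**What the plan says.** The pilot is described under Study Design, 2. Design, and powered under 2. Statistical Analysis, Recruitment & Retention Pilot.

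- **Design.** Subjects are "randomized to one of four groups (blocked within each study to ensure balanced groups"). The arms are SR, SR + IP, SR + CM and the combination: "4) SR + IP + CM (IC): In this group, subjects will receive the targeted text messages and receive CM". This is a 2x2 factorial structure.
- **Analysis.** The power paragraph plans a comparison of enrolment across the four arms and an examination of main and interaction effects.
- **Base rate.** "For SR arm, we expect a 28% of subjects who schedule an Intake will be eligible and enroll".
- **Main power claim.** "With the proposed sample of 576, we have >80% power" at alpha .05 "to detect a difference between the SR arm and the IP and CM arms of 12" per cent, "corresponding to an OR of 1.75".
- **Interaction claim.** 80% power at alpha .05 for a departure from additivity "corresponding to a ratio of odds ratios (ORR) of 5.5".

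The paragraph does not give the number per contrast, the sidedness of the tests, or the cell rates assumed for the interaction.

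**The concern.** Two statements in the paragraph do not sit with the design.

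First, a ratio of odds ratios of 5.5 is very large for a four-arm trial of this size. If each strategy alone raised enrolment from 28% to 40%, a positive ratio of 5.5 would put the combined arm at about 86%. Examining the strategies both independently and combined is a declared purpose of the design. A reader who believes the figure would conclude that the pilot can see only an implausibly strong interaction, and would discount that test.

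Second, the main power sentence names the SR arm as the comparator. The pilot's Aim 1 asks about the strategies alone and in combination, and its hypothesis is framed against standard recruitment. A reader will therefore take the >80% to cover IP v SR and CM v SR. If those contrasts have much less power, a null result in either would be over-read as evidence that the strategy does not work.

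**Working it through.** **Inputs.** From the documents: total 576, four balanced arms, SR rate 28%, difference 12 points, OR 1.75, ratio of odds ratios 5.5, alpha .05. Assumed: an equal split (576/4 = 144 per arm, 288 per factorial margin), two-sided tests, and no adjustment for study or covariates.

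**1. The plan's own main figure.** For 28% v 40%, OR = (0.40/0.60)/(0.28/0.72) = 1.714. Working back from OR 1.75 gives 40.5%, a difference of 12.5 points, which agrees with the stated 12 to rounding.

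Power = Φ[(0.12 − 1.96·s0)/s1], where s0 = √[p̄(1−p̄)(1/n1+1/n2)] and s1 = √[p1(1−p1)/n1 + p2(1−p2)/n2]. The unpooled version uses s1 in both places.

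Main effect, 288 v 288: p̄ = 0.34, s0 = 0.0395, s1 = 0.0392; (0.12 − 0.0774)/0.0392 = 1.09, power 86.2% (unpooled 86.5%). A logistic model gives 85.7% if the other factor has no effect and 87.6% if it has the same OR. The stated >80% is reproduced here.

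**2. The contrasts as worded, 28% v 40%, two-sided.**

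| Contrast | n | s0 | s1 | Power, pooled | Power, unpooled |
|---|---|---|---|---|---|
| SR v one active arm | 144 v 144 | 0.0558 | 0.0554 | 57.6% | 58.2% |
| SR v IP and CM pooled | 144 v 288 | 0.0490 | 0.0473 | 69.4% | 71.9% |
| SR v all three others | 144 v 432 | 0.0465 | 0.0442 | 74.4% | 77.4% |
| Factorial main effect | 288 v 288 | 0.0395 | 0.0392 | 86.2% | 86.5% |

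A single-arm contrast with SR needs about 244 per arm for 80% power. With 144 per arm it detects about 15.8 points (28% v 43.8%).

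The overall four-arm test is not a two-group difference. Its power depends on the combined arm's rate, which the plan does not give: 57% if that arm is also at 40%, 97% if it is at 53.3% (additive on the log-odds scale).

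**3. The interaction.** SE(log ratio) = √Σ 1/[144·p(1−p)] over the four cells, and power = Φ(|log ratio|/SE − 1.96). The fourth cell's odds are the additive odds times the ratio.

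Both main-effect ORs at 1.714:

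- Ratio 2.75: cells 28%, 40%, 40%, 75.9%. Sum = 0.0345 + 0.0289 + 0.0289 + 0.0379 = 0.130; SE 0.361; ln 2.75 = 1.012; 1.012/0.361 = 2.80; power 80.0%.
- Ratio 5.5: fourth cell 86.3%. Sum = 0.0345 + 0.0289 + 0.0289 + 0.0586 = 0.151; SE 0.389; ln 5.5 = 1.705; 1.705/0.389 = 4.39; power 99.2%.

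Across assumptions, two-sided:

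| Main-effect ORs | Direction | Ratio at 80% power | Power at 5.5 |
|---|---|---|---|
| 1 | positive | 2.76 | 99.6% |
| 1.714 | positive | 2.75 | 99.2% |
| 1.75 | positive | 2.76 | 99.2% |
| 1 | negative | 3.24 | 95.6% |
| 1.714 | negative | 2.70 | 99.5% |
| 1.75 | negative | 2.69 | 99.5% |

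Negative ratios are shown as reciprocals. One-sided tests lower the 80% value to between 2.40 and 2.77. For a positive interaction, a ratio of 5.5 at 80% power would need only about 53 to 59 per cell, roughly 210 to 237 in all. No variant at 144 per cell gives 5.5.

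**The case against.** The strongest defence concerns the main power claim. The same paragraph says that main and interaction effects will be examined, and its next sentence powers the interaction term, so the author may well have had the factorial margins in mind. On that reading >80% is correct. This stands, and the >80% should not be called false. It does not rescue the wording, because the reference group for a marginal effect is SR plus one active arm, not the SR arm.

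Sidedness is also unstated, and the hypothesis is directional. One-sided, SR against IP and CM pooled reaches about 80% at 28% v 40%, and 81-83% at OR 1.75. A single-arm contrast still falls short: 69% one-sided at 28% v 40%, 72% at OR 1.75.

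On the interaction, the defence is that the error is conservative. The design is more sensitive than claimed, so neither the sample size nor any test is put at risk, and the correct value depends on cell rates the plan omits. Both points are fair. They limit the consequence and require any corrected figure to carry its assumptions, but they do not make 5.5 reproducible.

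Finally, this is a recruitment pilot pooled over four studies and separate from the main trial's Aims 1 to 3.

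**Conclusion.** The interaction figure is wrong as written. With 144 per cell and a 28% SR rate, 80% power is reached at a ratio of about 2.75 (2.7 to 3.24 for a negative interaction, depending on the main effects), and power at 5.5 is 96% to over 99%. The plan understates its sensitivity to interaction.

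The >80% claim is attached to the wrong words. Of the two-group contrasts, it holds for the factorial main effects (86-87%) and for no two-sided comparison with the SR arm: 58% against one arm, 69-72% against IP and CM pooled, 74-77% against all three. These results assume equal allocation, two-sided alpha .05 and no covariate adjustment.

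Two stronger readings are tempting and are not supported:

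- **That the odds ratio is misstated.** The gap between 1.71 and 1.75 is within rounding of a 12-point difference.
- **That the outcome is circular.** The design text says "participants must meet all eligibility criteria for one of the four participating studies", while the outcome is meeting final eligibility, so one might infer 100% in every arm. The rest of the protocol rules this out. Initial screening is separated from eligibility determined at Intake, the SR texts go out before Intake, Table 1 lists percentage eligible at Intake, and the power paragraph uses scheduled Intakes as its denominator with 28% expected to enrol.

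**What to change.** Edit the pilot power paragraph in three places:

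1. Replace 5.5 with a ratio of odds ratios of about 2.75 for 80% power, and state the basis: 144 per cell, two-sided alpha .05, cells 28%, 40%, 40% and about 76% for a positive interaction. Add that a negative interaction needs 2.7 to 3.24, depending on the main effects.
2. Say that the >80% refers to the two factorial main effects, 288 v 288, with about 86% power for 28% v 40%.
3. Say that a contrast of one active arm with SR has about 58% power for the same difference, so that a null arm-to-SR result is reported with its confidence interval and not as evidence of no effect.

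The cost is text only. The sample size, randomization and planned analyses do not change, since main and interaction effects are already in the plan. The single-arm figure is less favourable than a reader would now assume; the interaction figure is more favourable.

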### **Sensitivity Analysis**

Given the substantial changes required to study procedures due to the COVID-19 pandemic, we will conduct a sensitivity analysis to evaluate the impact of the transition to remote visits on study results. We will utilize a 'clustering' approach

and assess the impact of clustering by analyzing outcomes with and without taking clustering into account: comparing the analysis that ignores clustering (i.e. assumes that the data are independent) to a method that will account for clustering (Thabane et al., 2013). To account for clustering, we will include a variable to compare subjects who completed the trial pre-COVID (all in-person) to those who completed the trial post-COVID (mostly remote visits with some in-person tasks).

### **Data Analysis.**

[name] will conduct analyses using Stata, SAS, or R-Language software. Preliminary analyses will determine whether data meet distributional assumptions, and use appropriate transformations where they do not. We will also determine whether subject characteristics (e.g., gender, nicotine dependence, depression, NMR) are associated with HIV status or outcomes using either cross-tabulation (chi-square), *t*-tests, or correlations. Variables showing potential to predict outcome ( $p=0.2$ ) will be tested for entry as controlling variables. In the event of items missing at random on survey measures, missing items will be imputed prior to calculating final scores using conditional means, estimated with an iterated version of Buck's method (Gleason and Staelin, 1975). Dropout and missed sessions present a more serious issue. The best way to deal with this more serious missing data is to avoid the problem in the first place by keeping subjects connected to the trial and motivated to complete measures. Our clinical trials have a record of >80% compliance and retention rates, thanks to our monitoring of participants and use of incentives to offset costs for travel. Primary analyses will include all subjects who went through the laboratory phase and began NRT treatment; we will assume those who provide incomplete smoking data are smoking. This assumption is the convention in smoking cessation research, but can attenuate the differences between study groups. We will, in addition, conduct analyses with other missing data assumptions, including a completers only analysis, to examine the sensitivity of the primary findings to our assumptions.

**Aim 1.** We will analyze neurocognitive data with multiple linear regression using a GLM framework. The outcomes will be cognitive deficits measured as a change in response values (see **Section D.4.d.** for description) due to abstinence challenge (24-h abstinence vs. smoking-as-usual). The hypothesized interaction effect of HIV+ status by abstinence condition will be tested by including dichotomous predictors, and examining the corresponding *z*-score. Although the groups will be matched on key variables, we may also include a small number of covariates (e.g., nicotine dependence, Shipley IQ) that show potential to control for error, admitted to the model at  $p=0.1$ . In conjunction with Aim 1, we will be estimating cognitive measures for the HIV+ group, within-subject correlations, and deficits that arise from abstinence challenge. We will summarize point estimates and provide 95% confidence intervals.

**Aim 2.** We will analyze point-prevalence quit rates using logistic regression. The hypothesized effect of HIV status (HIV+ vs. HIV-) will be tested by including a dichotomous term using the *z*-score. A small number of other potential controlling variables will be tested for inclusion ( $p=0.1$ ). Outcomes of the logistic regression analyses will be characterized by odds ratios (e.g., odds of quitting smoking) and 95% confidence intervals. Point-prevalence quit rates at EOT are the primary outcome. Secondarily, we will conduct logistic regression analyses for other assessments of quit rates, including prolonged and continuous abstinence.

**Aim 3.** Assuming that we find a significant effect of HIV+ status on abstinence at EOT, we will use a correlational and regression-based path model approach for examining mediation of HIV status effects (MacKinnon et al., 2007). Candidate mediators include five cognitive performance task measures (Neurocognitive Outcomes and Table 1), and will be represented as pre-post differences, continuously distributed and treated as normal. The effects of HIV status on candidate mediators, and of mediators on outcome will be assessed using a generalized path model (Stata GSEM), with the model reporting standardized coefficients. The path model partitions the effect of group on outcome into direct (and unexplained) effects versus mediated effects. We will then test the overall mediation hypothesis using the proportion of group effect explained [87, 88, 90] and the strength of each mediating pathway as follows. We will estimate the model for HIV status predicting abstinence without mediators, to estimate the direct effect of status in the unadjusted model ( $\hat{\beta}^*$ ). We will then test whether HIV status predicts the candidate mediators, and in turn, test whether mediators predict abstinence in an adjusted group effect model, and estimate the effect of HIV status in the mediator adjusted model ( $\beta^*$ ). Finally, we will calculate the proportion of HIV status effect explained, which is calculated as  $1 - (\hat{\beta}^* / \hat{\beta}^*)$ ; the standard error for this quantity is calculated using the delta method, and the mediation hypothesis will be tested using a *z*-test. The

primary analysis tested at  $\alpha=0.05$  will be global mediation – when all candidate mediators are included in the model, a significant proportion of the HIV status effect will be explained. We will also conduct a secondary analysis using products of the coefficients along each mediating path using a delta-method based z-test.

Exploratory Aim. Using the path model described above we will quantify the proportion of variance explained by each cognitive domain (e.g., executive function, verbal memory, and response inhibition) in the relationship between HIV status and abstinence rates. Since this test is exploratory, we do not have specific hypotheses about which domain will account for more variance and these analyses will be used for hypothesis generating for future work.

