#### 2. Design

**Main Study.** This study will use a prospective observational matched-design to test whether HIV+ smokers (vs. HIV-smokers) are more likely to experience cognitive deficits during nicotine withdrawal and whether these deficits are predictive of smoking relapse. As shown in Figure 1, adult treatment-seeking smokers (N=300; 150 HIV+ and 150 HIV-) will complete this 12-week study, which is divided into two phases: a pre-quit laboratory phase (weeks 0-2) and a treatment phase (weeks 3-12). Subjects will complete two laboratory sessions during the pre-quit phase: once following 24 hours of mandatory smoking abstinence and once while smoking-as-usual (order counter-balanced; abstinence biochemically confirmed). A cognitive task battery assessing working memory, sustained attention, and response inhibition will be administered during each session. During the treatment phase, subjects will receive standard smoking cessation treatment, including six sessions of brief individual counseling (weeks 3-8) and eight weeks of open-label transdermal nicotine (TN) patch treatment (weeks 4-12) [34]. The primary outcomes will be: 1) cognitive performance (e.g., verbal and working memory) following 24-hours smoking abstinence (vs. smoking-as-usual) during the pre-quit phase, and 2) 7-day point-prevalence, biochemically confirmed abstinence rates at end-of-treatment (EOT) for the treatment phase. Since randomization is not possible in this study, we will rely on inclusion criteria and matching to reduce the potential for confounding. More specifically, participants will be

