**Figure 1. Study Time Points and Assessments**

matched on age, race, education, and smoking rate.

**Rhythm Monitoring Sub-Study.** This sub-study will explore differences in arrhythmia burden between HIV+ and HIV-smokers and will also look at the relationship between arrhythmic burden and cognitive function. Fifty smokers (25 HIV+ and 25 HIV-) will be asked to wear a non-invasive rhythm monitoring device for two 2-week periods during the course of the study: for two weeks prior to smoking cessation treatment (weeks 2-4) and then two weeks near the end of treatment (weeks 8-10).

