#### Nicotine Metabolic Rate (3-HC/cotinine ratio/TNE).

One baseline blood sample will be collected at Intake and analyzed for nicotine metabolites to determine rate of nicotine metabolism. Nicotine is metabolized to cotinine and then to 3-HC by the P450 (CYP) 2A6 enzyme (Nakajima et al., 1996). The 3-HC/cotinine ratio is a stable measure of the rate of nicotine metabolism, which influences response to nicotine dependence treatments (Lerman et al., 2006; Patterson, Schnoll et al., 2008). Evidence also suggests that HIV-infected smokers metabolize nicotine faster than HIV-uninfected smokers (Earla et al., 2014). Therefore, the NMR will be evaluated as a potential moderator of abstinence-induced cognitive deficits and as a covariate in relapse analyses. Urinary concentrations of NIC and its nine metabolites will be analyzed using liquid chromatography tandem mass spectrometry, as described previously (T. Taghavi et al., submitted manuscript). Urine samples will be diluted and prepared using solid-phase extraction adapted from a previously established method (Miller et al., 2010). The limit of quantification was 1 ng/ml for all compounds. The primary outcome is Total nicotine equivalents (TNE), in nanomole per milligram creatinine, will be calculated as the molar sum of NIC and all nine metabolites (COT, 3HC, NIC-GLUC, COT-GLUC, 3HC-GLUC, NNO, CNO, NNIC, and NCOT) and will be corrected using scaled creatinine data. Urinary creatinine concentrations will be determined using a colorimetric assay according to protocol provided in the Creatinine Assay Kit (MAK080) purchased from Sigma-Aldrich (St. Louis, MO) with a SynergyMX Analyzer (BioTek, Winooski, VT). The

biosamples of individuals who complete the Pre-Quit visit will be sent to the laboratory of [name] at the University of Toronto for analysis. These analyses will be exploratory.

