## 2. Statistical Analysis

### **Power Analysis and Sample Size.**

Our study is a longitudinal between-subject design that seeks to test the following hypotheses: 1) that HIV+ smokers experience larger abstinence-induced cognitive deficits than HIV- smokers (Aim 1); 2) have lower quit-rates than HIV-smokers following standard treatment (Aim 2); and 3) that the association between HIV status and relapse is mediated by abstinence-induced cognitive deficits (Aim 3). We have designed our study to achieve 80% power, testing at a global  $\alpha=0.05$  for each of the hypothesis families (Figure 1). Our sample size of 300 was determined primarily by Aim 2. Based on prior work, we expect a ~15% difference in abstinence rates between HIV+ and HIV- smokers (Ferketich et al., 2013; Humfleet et al., 2013; Matthews et al., 2013; Silagy et al., 2004). With 150 HIV+ vs. 150 HIV- smokers, we have 80% power to detect a difference of ~15 percentage points in point-prevalence abstinence (60% vs. 45%, 50% vs. 35%, 40% vs. 25%), using a z-test on log-odds with a type 1 error of 5%. For Aim 1, we will test the HIV status by abstinence condition (24-h abstinence vs. smoking-as-usual) interaction for 5 cognitive measures using a linear regression with one between- and one within-subjects factor. We will correct for 5 tests using  $\alpha=0.01$ . We have 80% power to detect medium effect sizes (Cohen's  $d=0.4$ ). For Aim 3, we will test whether abstinence-induced cognitive deficits predict quit rates and, using SEM, test whether cognitive deficits mediate the effect of HIV status on quitting. The primary aim will be to test the overall fraction of the effect mediated, which will be tested at  $\alpha=0.05$ , which gives 80% power to detect small to medium effects ( $d=0.32$ ). For our exploratory aim, the component individual deficits will be treated as secondary and tested individually as part of an exploratory analysis, also with a 5% type 1 error. To characterize cognitive deficits in HIV+ smokers, 150 subjects will give us an estimate for each measure with a 95% CI that is 0.32 standard deviations wide (Upper – Lower limits). We will estimate the within-subject correlation for these as repeated measures, with a 95% CI that is 0.32 wide (Upper – Lower) if  $r=0$ , 0.24 if  $r=0.5$ , and 0.14 if  $r=0.75$ . Power was calculated using PASS software, NCSS, Kaysville, UT.

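### Covariates for the non-randomised HIV contrast are chosen by their p-value for the outcome; no adjustment set is fixed and the matching factors are not placed in any model

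*Combined protocol and SAP*

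**What the plan says.** Section 2, Design, makes the study observational: "Since randomization is not possible in this study, we will rely on inclusion criteria and matching to reduce the potential for confounding". The groups are to be "matched on age, race, education, and smoking rate". Target Population refers the reader to Accrual for the matching, but Accrual gives no ratio, caliper or matched sets.

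Data Analysis describes how covariates are picked:

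- **General step.** Characteristics such as gender, nicotine dependence, depression and NMR are checked for whether they "are associated with HIV status or outcomes using either cross-tabulation (chi-square") and other tests. Only those that look predictive of outcome at p=0.2 "will be tested for entry as controlling variables".
- **Aim 1.** "we may also include a small number of covariates (e.g., nicotine dependence, Shipley IQ) that show potential to control for error", admitted at p=0.1.
- **Aim 2.** "A small number of other potential controlling variables will be tested for inclusion", at p=0.1.
- **Aim 3.** No covariates are named. The mediation analysis goes ahead only if HIV status has a significant effect on abstinence.

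The Nicotine Metabolic Rate section separately describes NMR "as a covariate in relapse analyses" and cites evidence that HIV-infected smokers metabolise nicotine faster.

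The sensitivity analyses described deal with missing data and the move to remote visits. None deals with covariate choice.

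**The concern.** A confounder matters through two links: with HIV status and with the outcome. The plan examines both but acts only on the second, and only when that link reaches a p-value. With about 300 people and a binary outcome, a modest predictor often misses p=0.1. Several such variables, each somewhat imbalanced in the same direction, can be dropped one by one while their joint bias stays in the HIV coefficient. The reported standard error also takes no account of the selection.

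At stake is the Aim 2 odds ratio, the outcome that set the sample size. A false positive there would also open the Aim 3 mediation test.

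NMR shows the practical difficulty. One section treats it as a relapse covariate, another as a variable to be screened. Participants seen at the Bradbury-Sullivan Center are all HIV+ and have no blood drawn and no urine stored. If NMR passed the screen, a complete-case model would lose participants from the HIV+ group only, so a p-value would change the sample as well as the model.

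**Working it through.** **Inputs from the plan.** 150 per group; a logistic model for Aim 2; the test described as "using a z-test on log-odds with a type 1 error of 5" per cent (sidedness not stated, two-sided assumed); thresholds 0.2 and 0.1.

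**Inputs assumed, because the documents give none.** Quit rate 25% in both groups (no HIV effect); K independent standardised covariates; each differs between groups by a standardised mean difference (SMD) in the same direction; each has log odds ratio β per SD.

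**The plan's own figure.** The plan quantifies nothing on this point. Its Aim 2 power figure serves as a check on n and the test. For 40% vs 25%:
- log OR = ln[(0.40/0.60)/(0.25/0.75)] = ln 2 = 0.693
- SE = √(1/60 + 1/90 + 1/37.5 + 1/112.5) = 0.252
- power = Φ(0.693/0.252 − 1.96) = Φ(0.79), about 79%, against the stated 80%

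The other two pairs of rates give about 74%. That is a separate matter and does not bear on this point.

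**Simulation.** 5,000 data sets per row. The two-step rule screens each covariate on outcome at p<0.2, then enters it forward at p<0.1 with HIV status in the model. Cells show type I error, with mean bias in the HIV log OR in brackets.

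| K, SMD, β | Unadjusted | Two-step rule | All forced in |
|---|---|---|---|
| 4, 0, 0.20 | 4.7% (0.00) | 5.3% (0.00) | 5.1% (0.00) |
| 4, 0.2, 0.20 | 9.2% (0.15) | 6.3% (0.04) | 5.6% (−0.01) |
| 4, 0.3, 0.20 | 13.7% (0.24) | 7.4% (0.07) | 5.1% (0.00) |
| 4, 0.5, 0.20 | 30.4% (0.40) | 11.0% (0.13) | 5.5% (0.00) |
| 8, 0.2, 0.15 | 13.5% (0.24) | 7.6% (0.10) | 4.9% (0.00) |
| 6, 0.3, 0.20 | 26.2% (0.35) | 9.2% (0.11) | 5.2% (0.00) |

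The Monte Carlo standard error near 5% is √(0.05 × 0.95/5000) = 0.3 points.

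**Hand checks.**
- Unadjusted bias should be near K × SMD × β. For row 3, 4 × 0.3 × 0.20 = 0.24; simulated 0.236.
- A bias b with standard error s gives type I error Φ(−1.96 + b/s) + Φ(−1.96 − b/s). At 25% in both groups, s = √[2(1/37.5 + 1/112.5)] = 0.267. For row 3 unadjusted, b/s = 0.236/0.267 = 0.885, giving 14.3%; simulated 13.7%.
- For the two-step rule in row 4, b/s = 0.127/0.267 = 0.476, giving 7.6%; simulated 11.0%. Bias explains part of the excess. The rest fits a standard error that ignores selection.

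**Share of confounding left in.** In row 3, 0.070/0.236 = 30% of the unadjusted bias remains. In row 5, 0.101/0.236 = 43%.

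**Other settings.**
- One covariate (SMD 0.3, β 0.20): bias 0.027, type I error 5.2%.
- Four covariates at SMD 0.1 or 0.15: 5.2% each.
- SMD 0.3 with alternating directions: 6.4%, 6.4% and 7.6% for 4, 6 and 8 covariates. A further run with cancelling biases gave 5.9%, against 4.5% forced in.
- Forward entry at 0.2 instead of 0.1: 5.2 to 8.1% over the table's rows.
- Entering everything that passes the 0.2 screen, with no second step (separate runs, 30% quit rate): 5.0 to 5.6%.

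**The case against.** **The thresholds need not conflict.** A reader might infer that 0.2 and 0.1 contradict each other. The text does not support that: 0.2 decides what is tested for entry and 0.1 decides what is admitted, which reads naturally as a screen followed by entry. What stands is that the order is never stated, and that the reading changes the operating characteristics.

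**Design is the main control.** Inclusion criteria and matching on four factors come first, and the simulation credits matching only in so far as the assumed imbalances are residual. Good matching would remove much of the problem for those four. It does nothing directly for gender, dependence, depression or NMR, which the plan itself lists for checking, and the matching procedure is not described.

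**The inflation is assumed, not shown.** This is correct. No imbalance or covariate effect is given in the documents, and the larger figures need several imbalances in one direction. The rule also removes most of the unadjusted error. The check against HIV status would probably reveal several gaps of 0.3 SD, but the plan attaches no action to it.

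**Aims 1 and 3.** A reader might extend the figures to all three aims. The simulation covers Aim 2 only. Aim 1 analyses within-person change and uses covariates to reduce error. Aim 3 names no covariates, so nothing shows that its total effect comes from a p-value-selected model. Its link to this point is the requirement for a significant HIV effect.

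**Conclusion.** The concern holds as a conditional risk to Aim 2. The covariates for a non-randomised primary contrast depend on outcome p-values, imbalance by HIV status does not lead to entry, the matching factors are not stated to be in the models, and NMR has two roles.

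Over the imbalanced rows of the table, the two-step rule leaves a bias of 0.04 to 0.13 in the log odds ratio and a type I error of 6.3 to 11.0%, against 4.9 to 5.6% with all covariates forced in. Over all settings tried the bias runs from about 0.03 to 0.14; at the low end, a single confounder, the type I error is essentially nominal. With no imbalance there is no material inflation, and when the biases cancel it is small. For scale, a bias of 0.13 is 0.13/0.693 = 19% of the log odds ratio for 40% vs 25%.

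The documents do not support saying that confounding is present or that the type I error is in fact inflated. They support saying that the rule does not protect against it and that a better rule is available. For Aim 1 the point rests on the text alone.

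**What to change.** - **Aim 2.** Replace p-value selection with a pre-specified set forced into the model: age, race, education, smoking rate, sex and FTND.
- **NMR.** Give it one stated role in the relapse analyses. If it is a covariate, say how the HIV+ participants seen at Bradbury-Sullivan, who will have no value, are handled.
- **Aim 1.** Force in the matching factors and session order. Use Shipley IQ only in a sensitivity analysis: the protocol says the scale helps identify cognitive impairment and links such impairment to HIV, so adjusting for it could remove part of the effect under test.
- **Reporting.** Give the unadjusted result beside the adjusted one. Keep p-value selection, if at all, as a sensitivity analysis with the order of the two thresholds stated.
- **Matching.** Describe how it is done, since Accrual does not. Confirm that race is recorded; it is a matching factor but is not among the demographics listed for Intake.

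The cost is SAP wording, a few degrees of freedom and a slightly wider interval. No new assessments appear to be needed, subject to the check on race.
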